11.2 Information and data collection

Researchers should truthfully fill in the test results of the subjects and other relevant information, and ensure that the information is true and reliable. The specific

information and data to be collected are as follows :

(1) Sign informed consent ;

(2) Jaundice gene detection : Take out the special filter paper blood collection card, disinfect with alcohol and dry the heel blood collection site, collect heel peripheral blood, drop three drops on the filter paper.

(3) Detection of jaundice value by percutaneous jaundice meter : The family members of the subjects rented the percutaneous jaundice meter for free under the guidance of the doctor, and used the ' single measurement mode ' to measure the forehead, chest and inner thigh of the subjects every day for a total of 2 weeks.

(4) Collect demographic characteristics : screening number, name, gender, gestational age, date of birth, birth weight, body length, head circumference, mode of conception, Apgar score and parental information ;

(5) Perinatal information : parity, parity, mode of delivery, fetal membranes, amniotic fluid, placenta, umbilical cord, intrauterine distress, group B streptococcal infection, pregnancy complications such as gestational hypertension, diabetes, etc.

(6) Jaundice information : parents and newborns blood type, hemolysis three tests, feeding methods, percutaneous jaundice value, jaundice treatment and related test results ;

(7) Gene detection results : Collect gene analysis results, notes, etc.

12. Statistical processing

IBM-SPSS 26.0 statistical software and R language (Version 4.1.0) were used for statistical analysis of the test results. The carrying rate of common NHB-related gene mutation sites in neonates was counted, and the differences in the carrying rate of NHB-related pathogenic genes in neonates with different degrees of jaundice were compared. To explore the difference in the degree of jaundice carrying multiple and single jaundice-related genes. The measurement data were expressed as mean \pm standard deviation ($x \pm s$), and the t test was used for comparison between groups. The count data were expressed as values or rates (%), and the chi-square test was used for comparison between groups. Unconditional logistic multivariate regression analysis

was used to evaluate the correlation between genotype and clinical phenotype, and mediating variables were used to analyze the correlation between gene-gene interaction and genotype-phenotype.

13. data monitoring

(1) Case Report Form The case report form (CRF) was used in this study. The researcher ensures the authenticity, accuracy and integrity of the data in the original case of each enrolled (signed informed consent) newborn. The researcher or authorized researcher confirms and fills in the original medical record and submits it to the researcher / clinical coordinator. The data points in the original medical record are entered into the case report form system by the researcher / clinical coordinator.

(2) Data audit and locking After all data-related queries have been resolved, the main researchers, data managers, and statistical analysts will confirm the statistical analysis of the population, lock the database, and sign the audit report at the same time. The locked data must not be changed.

(3) Data privacy regulations All members of the research team, including lead researchers and their authorized researchers, must comply with all local and regional regulatory requirements and applicable privacy regulations (such as the ' Health Insurance Carriage and Liability Act ').

Each newborn participating in this study will be assigned a unique number and an institutional identifier.

All research data will be stored in a confidential electronic system and stored for at least 3 years after the completion of the study.

The coding table for recording neonatal information and research will be kept by the researcher (PI) in a locked file cabinet or in a password-protected database. Only researchers and their authorized researchers have the right to access the coding table.

The coding table that records the name of the hospital and the institution identification number will be saved by the research team in a locked file cabinet, which is only limited to access by limited research members.

The identity of each subject of observation should be kept confidential in research

reports and related publications.

14. adverse reactions

In this study, only 3 drops of neonatal heel peripheral blood were collected for genetic analysis and statistical analysis of percutaneous jaundice values. No human trials were involved. Family members were willing to know the genetic test results and the genetic test results were positive. Family members may have a certain psychological burden. We will provide free professional genetic counseling, as detailed as possible to inform the hazards of this genetic defect, treatment and other related information to help. Psychiatrists can be arranged for free psychological counseling if necessary.

15. Ethical approval

This clinical study follows the Helsinki Declaration (2013 edition), the ethical principles of human medical research and the relevant clinical research norms and regulations in China.

This clinical study was approved by the Research Ethics Committee / Institutional Review Boards (REC / IRBs).

This clinical study is an observational clinical study initiated by researchers. The clinical research protocol (including informed consent and case report forms, etc.) and other information provided to the family members or guardians of the newborn were reviewed and approved by the ethics committee of the clinical research team leader unit and the participating units.

16. informed consent

Before the start of the clinical study, the researchers completely and comprehensively introduced the purpose, process, method, and the interests and risks of the newborn to the parents or legal representatives who met the inclusion criteria. A written informed consent form was given to each parent or guardian of the newborn before enrollment, so that he / she had sufficient time to consider whether to consent to the collection of neonatal information to participate in this clinical study. After obtaining the informed consent of each newborn 's parent or legal representative and signing the informed consent form, researchers can begin to collect relevant data.

17. privacy protection

All members of the research team, including the primary researchers and their authorized researchers, must comply with all local and regional regulatory requirements and applicable privacy regulations.

Each newborn participating in this study will be assigned a unique number and an institutional identifier.

All research data will be stored in a confidential electronic system and stored for at least 3 years after the completion of the study.

The coding table for recording neonatal information and research will be kept by the researcher (PI) in a locked file cabinet or in a password-protected database. Only researchers and their authorized researchers have the right to access the coding table.

The coding table that records the name of the hospital and the institution identification number will be saved by the research team in a locked file cabinet, which is only limited to access by limited research members. The identity of each subject of observation should be kept confidential in research reports and related publications.

18. Research progress

September 01, 2023 to March 31, 2024: The samples were grouped and tested : (1) contact parents for informed consent ; (2) Collect 3 drops of heel peripheral blood samples, extract genomic DNA by magnetic bead genomic DNA extraction kit, and detect the samples by high-throughput sequencing technology ; (3) Collect neonatal clinical data and daily percutaneous bilirubin levels through the hospital inpatient system and the ' percutaneous jaundice instrument home monitoring + software doctor-patient interconnection ' method.

April 01, 2024 to June 30, 2024: Data analysis : (1) Statistics of neonatal common jaundice-related gene screening results : the positive rate of common jaundice gene screening (common positive disease cases, high-frequency pathogenic sites), the carrying rate of pathogenic mutations, the carrying rate of pathogenic genes with different degrees of jaundice, and the degree of jaundice carrying multiple and single jaundice pathogenic genes. (2) Combined with clinical data and data uploaded by

transcutaneous jaundice meter : Correlation analysis and comparison of jaundice-related gene detection results and jaundice clinical data to evaluate the feasibility of jaundice gene detection for neonatal hyperbilirubinemia screening.

July 01, 2024 - December 31, 2024: Write the conclusion report, complete the paper, submission and publication work.

19. Reference

- [1] Kong Yuanyuan, Zhang Yumin, Ding Hui. General situation and progress of neonatal disease screening. Chinese Journal of Preventive Medicine. 2011 , 45(10):954-956. DOI:10.3760/cma.j.issn.0253-9624.2011.10.023.
- [2] ZHANG Weiran, ZHAO Zhengyan. Research progress of neonatal disease gene screening. Chinese Journal of Pediatrics.2020 , 58(12):1033-1037. DOI:10.3760/cma.j.cn112140-20200614-00620.

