Excluded criteria	(1) Neonatal data with unclear clinical basic information ; (2) Lack of traceability core information data ; (3) data that the test results cannot be analyzed and interpreted ; (4) Sample collection is not qualified and unwilling to cooperate with re-sampling. (5) Newborns with severe deformity and severe lethal inherited metabolic diseases
Grouping and sample size	A total of 2000 neonates were included, including 500 cases of non-significant hyperbilirubinemia (TSB / TCB $<$ 205umol / L) ; (2) 500 cases of significant hyperbilirubinemia (205umol / L \leq TSB / TCB $<$ 342umol / L) ; (3) 500 cases of severe hyperbilirubinemia (TSB / TCB \geq 342umol / L) ; 4 Extremely severe hyperbilirubinemia 500 cases (TSB / TCB \geq 428umol / L).
data collection	(1) Basic information : gender, gestational age, date of birth, birth weight, height, head circumference, mode of conception, Apgar score and parents ' information ; (2) Perinatal information : parity, parity, mode of delivery, fetal

	
membranes, amniotic fluid, placenta, umbilical cord, intrauterine distress, group B streptococcal infection, pregnancy complications such as gestational hypertension, diabetes, etc.
 
(3) Jaundice information : blood types of parents and newborns, feeding methods, monitoring jaundice values, jaundice treatment methods and related test results ;
 
(4) Test results : Collect genetic analysis results, notes, etc.

Statistical processing	IBM-SPSS 26.0 statistical software was used to analyze the test results. Logistic multivariate regression analysis was used to evaluate the correlation between genotype and clinical phenotype, and mediating variables were used to analyze the correlation between gene-gene interaction and genotype-phenotype.
abbreviation	neonatal hyperbilirubinemia, NHB; total serum bilirubin, TSB; transcutaneous bilirubin, TCB; Principal Investigator, PI.

1. Research background

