This study will recruit subjects in the outpatient and inpatient departments of pediatrics, neonatology, and obstetrics in the South China Neonatal Genetic Screening Alliance (including cooperation units of 49 hospitals).

10. Clinical evaluation index

- (1) The carrying rate, positive rate, negative rate and high-frequency mutation sites of common NHB-related gene mutation sites in neonates ;
- (2) The difference in the carrying rate of NHB-related pathogenic genes in neonates with different degrees of jaundice ;
- (3) The difference of jaundice degree between carrying multiple and single jaundice pathogenic genes ;
- (4) Gene-gene interaction and genotype-phenotype correlation.

11. Methods

11.1 gene sequencing

A total of 24 genes were included in 29 NHB-related genetic diseases, including bilirubin metabolic disorders, congenital bile acid synthesis or transport disorders, red blood cell metabolic defects, lipid metabolic abnormalities, and metal metabolic abnormalities. The detected genes included ABCB11, ABCB4, ABCC2, ABCD3, ACOX2, AKR1D1, AMACR, ATP7B, ATP8B1, CYP7B1, G6PD, GBA, HBB, HSD3B7, JAG1, NOTCH2, NPC1, NPC2, NR1H4, SLC10A1, SLC25A13, SMPD1, TJP2 and UGT1A1. Gene and genetic disease related information refer to OMIM and Orphanet database.

Target gene sequence capture and library construction. Three drops of heel peripheral

blood were collected by filter paper, and genomic DNA was extracted by magnetic bead method. The target gene sequence was captured by multiplex PCR amplification method, covering all exon regions and adjacent intron regions ($\pm 50\text{bp}$) of the target gene. A total of 900 amplicons were designed for 24 genes and completed in two amplification systems. The target sequence library was obtained after amplification-purification-re-amplification-re-purification. The library was quantified using a Qubit[®] 3.0 fluorescence quantitative instrument (Thermo Fisher Scientific), and the library length was determined using an Aglient 2100 biological analyzer (Agilent) (228-378 bp).

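### The plan names no ethnic group or native place and compares carriage across severity groups unadjusted, so as written it cannot tell a gene effect from a difference in population mix

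*Combined protocol and SAP*

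**What the plan says.** **Data collected.** Section 11.2, item (4) gives the demographic list: "screening number, name, gender, gestational age, date of birth, birth weight, body length, head circumference, mode of conception, Apgar score and parental information". The Abstract's data-collection row has nearly the same list: "1) Basic information : gender, gestational age, date of birth, birth weight, height, head circumference, mode of conception, Apgar score and parents ' information". Neither names ethnic group, native place or residence, and neither says what the parental entry contains. Elsewhere, the parental data that are spelled out are blood types, in item (6) ("parents and newborns blood type, hemolysis three tests, feeding methods, percutaneous jaundice value, jaundice treatment and related test results"), and, for selected children, Sanger verification of the parents' loci (section 11.1).

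**Who is compared.** Section 8 fills four severity groups of 500. Section 9 recruits from outpatient and inpatient departments of the "South China Neonatal Genetic Screening Alliance (including cooperation units of 49 hospitals". The eligibility criteria in sections 4 and 5 do not restrict origin or residence.

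**What is compared, and how.** Section 10, index (2) is "The difference in the carrying rate of NHB-related pathogenic genes in neonates with different degrees of jaundice". For count data, section 12 says that "the chi-square test was used for comparison between groups". It also says that an unconditional multivariate logistic regression "was used to evaluate the correlation between genotype and clinical phenotype", without listing covariates.

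**Site.** Sections 13 and 17 state: "Each newborn participating in this study will be assigned a unique number and an institutional identifier". No analysis uses that identifier.

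**The concern.** Index (2) is a genetic association comparison among unrelated infants sampled by severity. If subpopulations differ in carriage, and also in severity for reasons other than the tested genes, the severity groups will differ in population mix. Carriage will then differ between groups even if the genes have no effect. Nothing in the sampling makes the mix equal across groups, and no planned analysis stratifies or adjusts for it. The 24 sequenced genes (section 11.1) are themselves the exposures under test, and the plan provides no ancestry markers for a genomic correction.

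At stake are index (2), the genotype-phenotype analysis in index (4), and objective (2), which would use the carriage results to choose mutation sites for large-scale screening.

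**Working it through.** **The plan's own figure.** Section 8 uses P = 30%, α = 0.05 and allowable error 2%. n = (1.96/0.02)² × 0.30 × 0.70 ≈ 2017, which agrees with the stated 2000 or so. This is a precision calculation for one proportion and does not bear on the present point.

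**Inputs from the documents.** Four groups of 500 (section 8); chi-square comparison (section 12), which for four groups has 3 df; α = 0.05.

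**Inputs assumed.** The documents give no subpopulation, no carriage by subpopulation and no mix by severity class. I assume two subpopulations with carriage c1 and c2 and no gene-severity association within either. The second makes up share s of each class. Two gradients in s across the four classes are tried: 30/37/43/50%, and one half as steep, 35/38.3/41.7/45%.

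**Formulas.** Carriage in class j: p_j = s_j·c2 + (1 − s_j)·c1. Noncentrality: λ = 500 × Σ(p_j − p̄)² / [p̄(1 − p̄)]. The false-positive rate is the probability that a noncentral chi-square with 3 df and noncentrality λ exceeds 7.815.

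**One case in full.** With c1 = 20%, c2 = 40% and the steeper gradient, p = 26.0, 27.4, 28.6 and 30.0%, and p̄ = 28%.
- Σ(p_j − p̄)² = 0.0004 + 0.000036 + 0.000036 + 0.0004 = 0.000872.
- λ = 500 × 0.000872 / (0.28 × 0.72) = 2.16.
- False-positive rate: 20.5%.

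**All cases.**

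| Assumed carriage, c1 v c2 | Shares 30/37/43/50% | Shares 35/38.3/41.7/45% | Same mix in every class |
|---|---|---|---|
| 20% v 40% | λ = 2.16, 20.5% | λ = 0.55, 8.5% | 5% |
| 25% v 35% | λ = 0.53, 8.3% | λ = 0.14, 5.8% | 5% |
| 3% v 12% (a single gene) | λ = 1.43, 14.8% | λ = 0.37, 7.2% | 5% |

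Rounding the 37/43% shares to exact thirds moves the largest figure from 20.5% to 20.9%, hence about 21%.

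**Sensitivity to stronger assumptions.** The result has no natural ceiling. Carriage of 15% v 45%, with the share of the higher-carriage subpopulation moving linearly from 30% to 70%, gives 24% v 36% carriage in the extreme classes and a false-positive rate of about 97%. Nothing in the documents makes that case more or less likely than those in the table. The answer is driven by the assumed contrast and gradient.

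**The case against.** Four points can be made against the concern.

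1. **The field may already be collected.** The parental entry is open-ended, and the case report form (section 13) is not in the documents. A reader might infer that origin is not recorded and so cannot be recovered at analysis. The documents do not show that; they show only that it is not itemised. Collection alone would not settle the matter, because no planned comparison uses it.

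2. **Hospital is recorded.** The institutional identifier would allow stratification by hospital, a crude proxy for place. A reader might therefore go too far in saying that gene effect and population mix can never be separated in these data. But no such stratification is planned, differences between families within a hospital would remain, and hospital may itself track severity through referral.

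3. **The size is all assumption.** This stands. Halving the gradient brings the rates down to 5.8–8.5%. Nor do the documents show that origin affects bilirubin other than through the tested genes, or that the recruited population is structured. A single regional alliance may narrow the variation. The 21% must not be read as an expected effect.

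4. **The study is exploratory, and the logistic model lists no covariates at all.** Both are true. They limit the severity of the point but leave the gap in the carriage comparison.

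**Conclusion.** The point holds as a gap in the plan as written: no origin variable is named, the parental entry is undefined, and the carriage comparison is unadjusted for origin or hospital. Following the plan to the letter, an investigator could not distinguish a gene effect from a difference in population mix.

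The size of any bias is unknown. In the six tabulated cases with a gradient, the nominal 5% false-positive rate becomes about 6% to 21%. It stays at 5% if the mix is equal in every class and is larger under more extreme inputs. These figures assume two subpopulations, no gene effect within either, and no allowance for hospital. They show what is possible, not what is likely.

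The change is worth making because it is cheap and easiest at enrolment, but confidence that the bias is material is low.

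**What to change.** - **Section 11.2, item (4), and the Abstract:** itemise the parental entry to include each parent's ethnic group and native place (province or prefecture). If the case report form already has these fields, say so.
- **Section 12, description:** tabulate both variables by severity class, so that a reader can see whether the mix differs.
- **Section 12, carriage comparison:** pre-specify a comparison stratified by origin (Mantel-Haenszel or stratified trend test), with a rule fixed in advance for sparse strata and for parents of different origin.
- **Section 12, logistic model:** name ethnic group and native place as covariates.
- **Hospital:** add it as a sensitivity analysis, not in the main model, because it may track severity through referral.

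Cost: two extra questions per parent, asked at consent, and a few degrees of freedom in the analysis. No new procedure and no change in sample size.

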Clinical research protocol

Project name: The effect and mechanism of gene variation on
neonatal hyperbilirubinemia

Leading unit: The Sixth Affiliated Hospital, Sun Yat-sen
University

Project leader: [name]

Department: Pediatrics

Research period: September 1, 2023 to December 31, 2024

Project number: EK-NHB-20230216

NCT No.: none.

Version No.: V1.0

Version Date: February 16, 2023

Abstract

object name	The effect and mechanism of gene variation on neonatal hyperbilirubinemia
goal of study	
(1) To analyze the carrying and pathogenicity of neonatal jaundice-related genes, and collect the sequencing data of jaundice-related genes (24 genes of 29 NHB-related genetic diseases) of 2000 newborns in the cooperative hospital to complete the construction of the gene database.
 
(2) To analyze the incidence of NHB-related genes, pathogenic mutations, suspected pathogenic mutations, and the carrying rate of unknown mutations in 2000 cases, and to count the distribution of high-frequency mutation sites in the population, so as to provide a scientific basis for the selection of mutation sites for large-scale neonatal hyperbilirubinemia gene screening.
 
(3) The influence of jaundice-related genes on neonatal jaundice was analyzed. The clinical data of newborns and the daily percutaneous bilirubin level were collected through the hospital hospitalization system and the " percutaneous jaundice instrument home monitoring + software doctor-patient interconnection " method to complete the construction of intelligent neonatal jaundice clinical database.
 
(4) Analyze the integrated monitoring data, statistically analyze the gene and jaundice clinical data of 2000 newborns, understand whether there is a difference in the carrying rate of related pathogenic genes in different degrees of jaundice, and explore whether there is a difference in the degree of jaundice carrying multiple and single jaundice pathogenic genes. To understand the

	correlation between gene polymorphism and clinical manifestations (phenotypic polymorphism) of neonatal hyperbilirubinemia, so as to better evaluate the effect of genes on neonatal jaundice.
research design	prospective observational study
Research period	September 2022 to December 2024
Participating	Newborns
Inclusion criteria	(1) Informed consent of parents or guardians ; (2) Age : 1-28 days, gestational age \geq 35 weeks ; (3) Birth weight \geq 2.5 kg and $<$ 4 kg.

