significant hyperbilirubinemia ($TSB / TCB < 205\text{umol} / \text{L}$), 500 cases of significant hyperbilirubinemia ($205\text{umol} / \text{L} \leq TSB / TCB < 342\text{umol/L}$), 500 cases of severe hyperbilirubinemia ($TSB/TCB \geq 342\text{umol/L}$) and 500 cases of extremely severe hyperbilirubinemia ($TSB/TCB \geq 428\text{umol} / \text{L}$).

4. Inclusion criteria

- (1) Informed consent of parents or guardians ;
- (2) Age : 1-28 days, gestational age ≥ 35 weeks ;
- (3) Birth weight ≥ 2.5 kg and < 4 kg.

5. Excluded criteria

- (1) Neonatal data with unclear clinical basic information ;
- (2) Lack of traceability core information data ;
- (3) data that the test results cannot be analyzed and interpreted ;
- (4) Sample collection is not qualified and unwilling to cooperate with re-sampling.
- (5) Newborns with severe deformity and severe lethal inherited metabolic diseases

6. termination criteria

- (1) The family members of the newborn included in the study requested termination at any time ;
- (2) The relevant management departments require termination.

7. outcome index

Through the comprehensive analysis of genetic variation information and jaundice clinical data, the carrying rate of pathogenic genes of common hereditary jaundice diseases in newborns was counted, and the difference of carrying rate of pathogenic genes in different degrees of jaundice was understood. To explore whether there is a difference in the degree of jaundice carrying multiple and single jaundice pathogenic genes, and to analyze the correlation between gene polymorphism and clinical manifestations (phenotypic polymorphism) of neonatal hyperbilirubinemia.

8. Grouping and sample size

This study is a prospective observational study. According to the positive mutation rate of NHB-related genes in neonatal hyperbilirubinemia, P is about 30 %, the test level α

= 0.05 and the allowable error $\delta = 2 \%$, n (sample size) = ($U\alpha / \delta$) $2 * p * (1 - P) \approx$ 2000 cases. A total of 2000 neonates were included, including 500 cases of non-significant hyperbilirubinemia ($TSB / TCB < 205\text{umol} / L$) ; (2) 500 cases of significant hyperbilirubinemia ($205\text{umol} / L \leq TSB / TCB < 342\text{umol} / L$) ; (3) 500 cases of severe hyperbilirubinemia ($TSB / TCB \geq 342\text{umol} / L$) ; (4) Extremely severe hyperbilirubinemia 500 cases ($TSB / TCB \geq 428\text{umol} / L$) .

9. Recruiting

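### Jaundice degree is compared between carrier groups in a sample fixed at 500 per bilirubin group, and section 12 makes no allowance for that sampling

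*Combined protocol and SAP*

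**What the plan says.** Section 8 sets the composition of the sample by bilirubin: "A total of 2000 neonates were included, including 500 cases of non-significant hyperbilirubinemia", then 500 from 205 to below 342 umol/L, 500 at 342 or above, and finally "Extremely severe hyperbilirubinemia 500 cases" at 428 or above. The same counts appear in the Abstract and in sections 1 and 3.

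Section 10, index 3, then takes severity as the outcome: "The difference of jaundice degree between carrying multiple and single jaundice pathogenic genes".

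Section 12 repeats that aim without naming a test, model or effect measure for it. The general rules that follow are mean and standard deviation for measurement data, "and the t test was used for comparison between groups", and for categories "The count data were expressed as values or rates (%), and the chi-square test was used for comparison between groups". Unconditional logistic regression "was used to evaluate the correlation between genotype and clinical phenotype", but its outcome is not defined and it is not tied to index 3. Section 12 mentions no weights or sampling fractions.

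The stated purpose goes beyond detecting a difference. Goal (4) in the Abstract ends "so as to better evaluate the effect of genes on neonatal jaundice", and section 3 lists the multiple-versus-single comparison among the steps towards judging whether gene screening is feasible.

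**The concern.** The sample is selected on the variable that index 3 then summarises. When enrolment fixes the share of newborns at each bilirubin level, an unweighted mean or percentage of bilirubin severity reflects that choice as well as biology. If genes had no effect, every genotype group would be expected to show 25% in each severity group, whatever the true shares among newborns.

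A reported difference in umol/L, or the share of multiple carriers in the top group, would naturally be read as what carrying a further gene does in newborns. That reading matters for a screening judgment, and neither figure supports it. The plan does not record how many eligible newborns were seen in each severity group, so the figures could not be corrected afterwards.

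The problem is confined to index 3 and to any regression that merges severity groups. Index 2, the carriage rate within each severity group, is not affected.

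**Working it through.** **The plan's own figure.** Section 8 computes n = (1.96/0.02)² × 0.30 × 0.70 = 2017, stated as about 2000. It reproduces, but it concerns the precision of one carriage proportion and has no bearing on index 3.

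**Inputs.** From the documents: cut-points 205, 342 and 428 umol/L, 500 per group, and for carriage "According to the positive mutation rate of NHB-related genes in neonatal hyperbilirubinemia, P is about 30" per cent. Everything else is assumed, because no source distribution is given:
- 70% non-carriers, 24% single and 6% multiple carriers. The 30% is the plan's rate for hyperbilirubinemia, applied here to the whole source.
- Multiple carriers 20 umol/L above single carriers.
- The severe group taken as 342 to below 428.
- Jaundice degree taken as the bilirubin value used for grouping.
- Selection within a severity group does not depend on genotype.

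**Method.** If severity group k has source share π_k, equal enrolment multiplies its members by w_k = 0.25/π_k. Carrier distributions and means are recomputed with those multipliers.

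**Worked example.** Normal source, non-carrier mean 200, SD 100, single carriers +15, multiple carriers +35:

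| | <205 | 205 to <342 | 342 to <428 | ≥428 |
|---|---|---|---|---|
| Source share π_k | 0.497 | 0.415 | 0.074 | 0.0135 |
| Multiplier w_k | 0.50 | 0.60 | 3.38 | 18.5 |
| Single, source | 46.0% | 43.8% | 8.6% | 1.7% |
| Single, sample | 21.2% | 24.2% | 26.5% | 28.2% |
| Multiple, source | 38.2% | 47.6% | 11.6% | 2.7% |
| Multiple, sample | 14.1% | 21.0% | 28.6% | 36.4% |

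- *Mean difference.* Sample means are 321.2 (single) and 352.3 (multiple). The difference is 31.0 against a true 20, and 31.0/20 = 1.55.
- *Odds ratio, ≥428 against <205.* Source: (2.68/38.21)/(1.66/46.02) = 1.95. Sample: (36.36/14.07)/(28.15/21.21) = 1.95. The three ratios against the lowest group are 1.31, 1.63 and 1.95 in both source and sample, because the multipliers cancel.
- *Merged outcome ≥205.* Source: (61.79/38.21)/(53.98/46.02) = 1.38. Sample: (85.93/14.07)/(78.79/21.21) = 1.64.
- *Merged outcome ≥428.* Source 1.63, sample 1.46. Merging can distort in either direction.

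At mean 250 and SD 120, the mean difference appears 1.27 times as large, and 34% of multiple carriers fall at ≥428 against 11.7% in the source.

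**Range.** Six means (150–260), eight SDs (50–120), single carriers +0, +10 or +20, keeping settings where ≥428 is at least 1% of the source:

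| Source | Settings | Apparent/true difference |
|---|---|---|
| Normal | 61 | 1.25–2.18 |
| Gamma or lognormal, constant shift | 192 | 0.57–2.25 (below 1 in 76) |
| Same, SD at most half the mean | 130 | 0.84–2.25 (below 1 in 17) |
| Gamma or lognormal, proportional effect | 198 | 1.27–2.66 |

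A carrier share of 20–40% moves the normal range only to 1.24–2.21. A second set of normal assumptions (mean 180–220, SD 60–80, 3% multiple carriers, true difference 10–40) gives about 1.4 (54.6/40) to 3.2 (31.5/10). There the top group is under 1% of the source.

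**Check on drawn samples.** In 1000 samples of 4 × 500 from the worked example, the raw mean difference averaged 30.5, and 19.9 after weighting back to the source. Multinomial odds ratios averaged 1.32, 1.62 and 1.95. With no true difference, the t test rejected in 4.8% and chi-square in 5.1%.

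**The case against.** The strongest reply is that index 3 mostly asks whether a difference exists, and for that question the t test and chi-square are valid. That stands. The concern covers reported magnitudes, not the tests. But section 12 says data will be expressed as means and rates, so magnitudes will be reported.

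Second, section 12 never commits index 3 to the t test, and the planned logistic regression could be read as covering it. It is true that the index 3 analysis is unspecified. The general rules are nevertheless all that section 12 offers after stating the aim, and the regression resists the sampling only if the four groups stay separate, which the plan does not require.

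Third, the link to screening feasibility is looser in section 18, where index 3 and the feasibility judgment sit under different items. That is fair. Section 3 does connect them, though without saying how an effect size would be used.

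Fourth, quota is not the plan's word, and the filling of the groups is not described. Even so, four equal counts of 500, one of them at 428 umol/L or above, cannot be presumed to be a natural distribution.

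Fifth, the size rests on assumptions and the range includes no distortion. Section 11.2 also collects two weeks of daily readings at three body sites, and the plan does not say which value defines jaundice degree. Both points stand. They limit what can be said about size, not about existence.

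**Conclusion.** The concern holds. As written, the plan would produce mean differences and severity percentages for index 3 that depend on the fixed group sizes. This follows from the design and needs no assumed distribution.

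Neither the size nor the direction of the distortion in the mean difference is assured. It inflates under every normal and proportional-effect setting examined, and can shrink under a skewed source with a constant shift. The severity percentages are far from the source values in the examples.

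Null tests and odds ratios between separate severity groups are unaffected, provided that selection within a group does not depend on genotype. The plan should be changed, because its figures would otherwise invite a population reading. Confidence is medium, since the index 3 analysis is unspecified and every size figure is illustrative.

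**What to change.** 1. Reconcile the ≥342 and ≥428 groups, which overlap as written, so that the four groups are mutually exclusive.
2. State in section 12 that index 3 is analysed by the planned logistic regression, with the four severity groups as a multinomial outcome and multiple versus single carriage as predictor. Report odds ratios with 95% confidence intervals against the non-significant group.
3. Do not merge groups into a yes/no outcome without weights. Use a single adjacent-category slope only if one slope fits.
4. State that raw mean differences and severity percentages among carriers describe the sample only, unless weighted by recorded sampling fractions per severity group.

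These are wording changes to a method already planned. Weighting costs more, because sites must log how many eligible newborns they saw in each severity group.

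The drawbacks are results on the odds-ratio scale instead of umol/L, and limited precision. In the worked example about 23, 34, 47 and 60 multiple carriers and 111, 127, 139 and 147 single carriers are expected across the four groups. For the top group the standard error of the log odds ratio is √(1/60 + 1/23 + 1/147 + 1/111) ≈ 0.276. The three odds ratios would be about 1.31 (0.73–2.35), 1.63 (0.93–2.84) and 1.95 (1.13–3.34).
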